14.3 Primary/Exploratory Endpoints/Hypotheses and Analytical Methods

14.3.1 Primary endpoint

The primary objective of this study is to evaluate the feasibility of randomizing patients to either intensive or non-intensive induction and post remission chemotherapy. We will consider randomization feasible (i.e. a subsequent, larger study would be designed as a randomized trial) if the true proportion of patients willing to be randomized is 60% or higher. With 50 patients in a feasibility study and accounting for the sample variation associated with 50 patients, we will consider randomization feasible if at least 52% of the patients agree to be randomized (i.e. 26 or more of 50 patients agree to be randomized). If the true proportion willing to be randomized is 60%, the probability of observing 52% or more willing to be randomized is 90%. The probability of having 26 or more of the 50 patients agree to be randomized is only 6% if the true randomization agreement rate is 40%, and <1% if the true randomization agreement rate is 30% or lower, providing good operating characteristics not only to avoid a false negative result but also a false positive result. If one treatment arm closes prematurely (see section on monitoring below), we will conclude that randomization is not feasible, and the remaining patients will be treated on the remaining arm. Continuation of enrollment into that remaining arm will allow us to gain additional experience and provide more precise estimates of treatment efficacy and treatment-related toxicities.

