14.3.2 Exploratory endpoints

This pilot study will use exploratory, descriptive, and observational methods to

- 1) Evaluate the attitude of patients and physicians toward randomization and explore reasons for treatment preference
- 2) Evaluate whether the ability to assess fitness for intensive chemotherapy can be improved by an augmented treatment-related mortality (TRM) score that includes additional (co-

morbidity) factors, and to compare the ability of physicians of the prediction algorithm(s) and physician to assess the likelihood of early death

3) Estimate differences between patients treated with lower-intensity G-CLAM and those treated with higher-intensity G-CLAM with regard to anti-leukemic efficacy (response, duration of response) and survival, QOL, and medical resource utilization as well as care cost

Importantly, this trial is not powered to detect statistically significant differences between the study arms for these clinically important endpoints. Rather, the primary goal is to estimate outcomes with both treatment intensities to inform a subsequent larger study, should follow-up investigation appear warranted.

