Early death: If the number of early deaths is 5 or higher, accrual will stop with the conclusion that the arm is too toxic for further randomization. If the true early mortality rate is 30% or less, the probability of observing 5 or more early mortality events is 15%.

Inefficacy: If there are 0 patients with MRD^{neg} CR, accrual will stop with the conclusion that the arm is not efficacious enough for further randomization. If the true MRD^{neg} CR rate is 22%, the probability of observing 0 MRD^{neg} CRs in 10 patients is 8%.

Between-arm monitoring for efficacy and early mortality

After enrollment of at least 10 patients in each arm (at which point one arm may have more than 10 patients accrued due to slower accrual in one arm), we will compare the two arms for relative mortality and efficacy. If, based on Fisher's exact test, the early mortality rate is significantly higher in one arm at the alpha =10% level (this criterion will be met if, for example, both arms have accrued 10 patients one arm has 0 early mortality events and the other arm has 4), accrual will stop in that arm with the conclusion that the arm with the higher early mortality rate is too toxic for further randomization. In addition, if based on Fisher's exact test, the MRD^{neg} CR rate is significantly higher in one arm compared to the other at the alpha = 10% level (for example, this criterion will be met if both arms have accrued 10 patients and one arm has 2 MRD^{neg} CRs and the other has 7), the accrual will stop in that arm with the conclusion that the arm with the lower MRD^{neg} CR rate is not efficacious enough for further randomization.

If accrual does not stop in both arms, up to a total of 50 patients will be accrued.

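### The between-arm MRDneg CR rule stops accrual in the arm with the higher rate but faults the arm with the lower rate

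*Combined protocol and SAP*

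**What the plan says.** The between-arm part of Section 14.4 contains two rules built on the same sentence frame.

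- **Early mortality.** The trigger is a significantly higher rate in one arm (Fisher's exact test, 10% level). The consequence: "accrual will stop in that arm with the conclusion that the arm with the higher early mortality rate is too toxic for further randomization".
- **MRDneg CR.** The trigger: "the MRD^{neg} CR rate is significantly higher in one arm compared to the other at the alpha = 10% level". The consequence: "the accrual will stop in that arm with the conclusion that the arm with the lower MRD^{neg} CR rate is not efficacious enough". The worked example is 2 versus 7 MRDneg CRs with 10 patients per arm.

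Three other statements bear on the point.

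- The within-arm inefficacy rule, given for each arm in Section 14.4: "If there are 0 patients with MRD^{neg} CR, accrual will stop with the conclusion that the arm is not efficacious enough for further randomization".
- Section 14.3.1, on premature closure of an arm: randomization is declared not feasible and "the remaining patients will be treated on the remaining arm".
- Section 14.4, on the timing of the look: "at which point one arm may have more than 10 patients accrued due to slower accrual in one arm".

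**The concern.** For early mortality a higher rate is worse, so trigger, action and conclusion all refer to the same arm. For MRDneg CR a higher rate is better. The conclusion was turned round to name the lower-rate arm, but the action clause kept the wording of the mortality rule and still points to the higher-rate arm. The sentence therefore closes one arm and gives a reason for closing the other.

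The rule decides which arm stays open. Followed literally, it would close the better-performing arm and, through Section 14.3.1, treat everyone enrolled afterwards on the arm just judged not efficacious enough. Further information would also accumulate on the wrong arm, although Section 14.3.2 says of these endpoints that "the primary goal is to estimate outcomes with both treatment intensities to inform a subsequent larger study".

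**Working it through.** **1. Which arm each clause names**

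| Clause | Early-mortality rule | MRDneg CR rule |
|---|---|---|
| Trigger | arm with higher rate (worse) | arm with higher rate (better) |
| Action (literal) | stop the higher-rate arm | stop the higher-rate arm |
| Conclusion | higher-rate arm too toxic | lower-rate arm not efficacious enough |
| Same arm throughout? | yes | no |

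No other section restates the direction of the between-arm MRDneg CR rule. The within-arm rule agrees with the conclusion and not with the literal action.

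**2. The plan's own examples reproduce**

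Inputs are the two examples in Section 14.4, with 10 patients per arm.

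- *2/10 versus 7/10.* With 9 responders among 20, P(X = k) = C(10,k)·C(10,9−k)/C(20,9), and C(20,9) = 167,960. P(2) = 45·120/167,960 = 0.0321, P(1) = 10·45/167,960 = 0.0027 and P(0) = 10/167,960 = 0.0001. The sum is 0.0349 one-sided. By symmetry the two-sided p is 0.0698, so the criterion is met. The next table, 2/10 versus 6/10, gives a two-sided p of 0.170 and does not meet it.
- *0/10 versus 4/10* (the mortality example). C(10,4)/C(20,4) = 210/4,845 = 0.0433 one-sided, or 0.0867 two-sided. The criterion is met.

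The trigger is therefore as stated, and only the direction of the action is at issue. In the first example the literal action closes the 7/10 arm and keeps the 2/10 arm open.

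**3. Patients left for the open arm**

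Up to 50 are enrolled. The plan allows unequal arms at the look.

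- Arms of 10 and 10: 50 − 20 = 30
- Arms of 10 and 15 (assumed): 50 − 25 = 25
- Arms of 10 and 20 (assumed): 50 − 30 = 20

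**4. How often the rule would fire**

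This sums the binomial probabilities of all outcomes with 10 per arm and two-sided Fisher p ≤ 0.10. The plan does not state sidedness. One arm is at 22%, the plan's historical rate (8/37); rates of 40% to 60% for the other arm are assumptions.

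| True rates | P(rule fires) | of which truly better arm observed higher |
|---|---|---|
| 22% / 22% | 0.032 | not applicable |
| 22% / 40% | 0.1115 | 0.1099 |
| 22% / 50% | 0.2228 | 0.2225 |
| 22% / 60% | 0.3847 | 0.3847 |

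In the unequal cases at least 0.1099/0.1115 = 98% of triggers would, read literally, close the truly better arm.

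**5. Clash with the within-arm rule**

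Suppose the MRDneg CR counts are 0/10 and 4/10 (p = 0.087). The within-arm rule closes the 0/10 arm. If the between-arm comparison is also made, its literal action closes the 4/10 arm, and both arms are shut. The chance of 0/10 at 22% is 0.78^10 = 0.083. Multiplied by the chance of at least 4/10 in the other arm, this is 0.051, 0.069 or 0.079 at assumed rates of 40%, 50% or 60%.

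**6. Precision (exact 95% intervals)**

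- 7/10: 35% to 93%
- 28/40: 53% to 83% (for scale, the same proportion if all 30 remaining patients went to that arm)
- 2/10: 3% to 56%

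**The case against.** The strongest reply is that the sentence corrects itself. It gives its reason for stopping, and nobody could carry out the literal action without contradicting that reason. The within-arm rules and the opening of the within-arm text in Section 14.4, which speaks of early stopping for inefficacy, point the same way. Section 12.0 also has independent committees review stopping rules. On this view the defect is a slip of reference that needs only clarification. It is right that the intent can be inferred and that staff would probably notice. But those other passages show intent without restating the between-arm direction, and following the rule correctly still means setting aside its operative clause.

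Three further points qualify the illustrations.

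- Any one-arm closure costs precision in the closed arm, and 2/10 gives an interval about as wide as 7/10. The wording affects which arm loses precision, so the main cost is where later patients are treated.
- Section 14.4 says regimens are compared among randomized patients, while the first 10 per arm may include non-randomized ones. If only 6 per arm entered the test (an assumption), the four firing probabilities would fall to 1%, 6%, 12% and 22%.
- Closure of both arms depends on the between-arm test still being run after the within-arm rule has closed one arm, which the plan does not say.

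None of these removes the contradiction.

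**Conclusion.** The concern holds. The action and the conclusion of the between-arm MRDneg CR rule name different arms. Read literally, the plan's own example closes the 7/10 arm and treats at most 30 further patients on the 2/10 arm.

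The contradiction rests on the text alone. The firing probabilities (3% at equal rates, 11% to 38% at the assumed unequal rates) rest on 10 analysed patients per arm, a two-sided test and the assumed 40% to 60%.

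The feasibility conclusion is not affected by the wording, because Section 14.3.1 declares randomization not feasible whichever arm closes. The threshold of 26 of 50 and its stated probabilities also stand. Because this is an operative arm-closing rule, it must be corrected.

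**What to change.** In Section 14.4, make the action clause name the arm that the sentence's own conclusion faults. For example: *accrual will stop in the arm with the lower MRDneg CR rate, and that arm will be judged insufficiently efficacious for further randomization.* The early-mortality sentence needs no change.

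The cost is one phrase. The test, alpha, sample size, worked example and every stated figure stay as they are.

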14.5 Ethnic and Gender Distribution Chart

All eligible patients will be included in this study without regard to gender or ethnicity. The incidence of AML is slightly higher in men, so it is expected that the distribution of these patients will reflect a slight male predominance of the disease as well as the general demographic distribution of AML patients seen at our institution. Up to 50 patients with newly diagnosed AML or analogous high-grade neoplasms will be enrolled in this study.

Projected Target Accrual
ETHNIC AND GENDER DISTRIBUTION CHART

TARGETED / PLANNED ENROLLMENT: Number of Subjects			
Ethnic Category	Sex / Gender		
	Females	Males	Total
Hispanic or Latino	1	1	2
Not Hispanic or Latino	20	28	48
Ethnic Category Total of All Subjects*	21	29	50
Racial Categories			
American Indian / Alaska Native	0	0	0
Asian	1	1	2

Native Hawaiian or Other Pacific	0	0	0
Black or African American	1	1	2
White	19	27	46
More Than One Race	0	0	0
Racial Categories: Total of All	21	29	50

15.0 INVESTIGATOR OBLIGATIONS

The PI is responsible for the conduct of the clinical trial at the site and is responsible for personally overseeing the treatment of all study subjects. The PI must assure that all study site personnel, including sub-Investigators and other study staff members, adhere to the study protocol and to all applicable regulations and guidelines regarding clinical trials both during and after study completion.

All subjects are informed of the nature of the program, its possible hazards, and their right to withdraw at any time, and each subject signs a form indicating their consent to participate prior to receiving any study-related procedures.

16.0 ADMINISTRATIVE AND REGULATORY CONSIDERATIONS

16.1 Protocol Interpretation and Compliance

The procedures defined in the protocol are carefully reviewed by the PI and his/her staff prior to the time of study initiation to ensure accurate representation and implementation. Protocol amendments, if any, are reviewed and implemented promptly following IRB/EC and relevant Competent Authorities approval.

16.2 Ethical Considerations

The Investigator agrees to conduct this study in accordance with applicable United States FDA clinical trial regulations and guidelines, the ICH (E6) GCP guidelines, the IRB/EC and local legal requirements and with the Declaration of Helsinki (1989). The Investigator will conduct all aspects of this study in accordance with all national, state, and local laws of the applicable regulatory agencies.

16.3 Informed Consent

The PI and qualified designees assume the responsibility of obtaining written Informed Consent for each subject or the subject's legally authorized representative before any study-specific procedures are performed.

Subjects meeting the criteria set forth in the protocol will be offered the opportunity to participate in the study. To avoid introduction of bias, the Investigator must exercise no selectivity with regard to offering eligible subjects the opportunity to participate in the study. Subjects or parents/legal guardians of all candidate subjects will receive a comprehensive explanation of the proposed treatment, including the nature of the therapy, alternative therapies

available, any known previously experienced adverse reactions, the investigational status of the study drug, and other factors that are part of obtaining a proper Informed Consent. Subjects will be given the opportunity to ask questions concerning the study, and adequate time to consider their decision to or not to participate. Informed Consent will be documented by the use of a written Consent Form that includes all the elements required by FDA regulations and ICH guidelines. The form is to be signed and dated by the subject or subject's legally authorized representative and by the person who administers the consent process. A copy of the signed form will be given to the person who signed it, the original signed Consent Form will be filed with the subject's medical records, and copy maintained with the subject's study records. The date and time of time of the Informed Consent must be recorded in the source documents. If an amendment to the protocol changes the subject participation schedule in scope or activity, or increases the potential risk to the subject, the Informed Consent Form must be amended. Any amended Informed Consent must be reviewed by the Sponsor or designee and approved by the IRB/EC prior to use. The revised Informed Consent Form must be used to obtain re-consent from any subjects currently enrolled in the study if the subject is affected by the amendment, and must be used to document consent from any new subjects enrolled after the approval date of the amendment.

16.4 Institutional Review Board/Ethics Committee

The PI will assure that an appropriately constituted IRB/EC that complies with the requirements of 21 CFR Section 56 or written assurance of compliance with ICH (E6) guidelines will be responsible for the initial and continuing review and approval of the clinical study. Before initiation of the study, the PI or designee will forward copies of the protocol and Consent Form to be used for the study to the IRB/EC for its review and approval. The PI or designee will also assure that all changes in the research activity and all unanticipated problems involving risks to human subjects or others will be reported promptly to the IRB/EC, and that no changes will be made to the protocol without prior IRB/EC approval, except where necessary to eliminate apparent immediate hazards to human subjects. The Investigator or designee will be responsible for submitting periodic progress reports to the IRB/EC at intervals appropriate to the degree of subject risk involved in the study, but not less than once per year and at the completion or termination of the study.

17.0 STOPPING THE STUDY

The study will terminate as described in section 10.0. The Principal Investigator and the IRB reserve the right to terminate this study at any time.

19.0 APPENDICES

APPENDIX A: TREATMENT-RELATED MORTALITY (TRM) SCORE

Calculation of Simplified Treatment-Related Mortality (TRM) Score

Includes covariates: performance status (PS), age, platelet count, albumin, secondary AML, white blood cell count (WBC), peripheral blood blast percentage, and creatinine

Score = $100/(1+e^{(-x)})$, with $x = -4.08 + 0.89*PS + 0.03*age - 0.008*platelet count - 0.48*albumin + 0.47*(have secondary AML) + 0.007*WBC - 0.007*(peripheral blood blast percentage) + 0.34*creatinine$

Probability of TRM Above and Below Various Simplified TRM Score Cut-offs

TRM Score Interval	Patients below/within/above TRM Score Interval (%)	TRM Probability if below TRM Score Interval (%)	TRM Probability if within TRM Score Interval (%)	TRM Probability if above TRM Score Interval (%)
0 – 1.9	0/20/80	-	1	12
1.91 – 3.9	20/20/60	1	2	16
3.91 – 6.9	40/20/40	1	7	20
6.91 – 9.2	60/10/30	3	7	24
9.21 – 13.1	70/10/20	4	12	31
13.11 – 22.8	80/10/10	5	20	41
22.81 – 100	90/10/0	6	41	-

From: Walter RB, Othus M, Borthakur G, Ravandi F, Cortes JE, Pierce SA, Appelbaum FR, Kantarjian HM, Estey EH. Prediction of early death after induction therapy for newly diagnosed acute myeloid leukemia with pretreatment risk scores: a novel paradigm for treatment assignment. *J Clin Oncol.* 2011;29(33):4417-4424.

APPENDIX B: DOSE MODIFICATION TABLE

For patients who experienced \geq Grade 3 non-hematologic toxicities excluding neutropenic fever and infections during the first induction, the following dose reduction can be considered for the next course

High-Dose Arm

Drug	Dose Reduction #1	Dose Reduction #2
G-CSF	No change	No change
Cladribine	Cladribine 4 mg/m ²	Cladribine 3 mg/m ²
Cytarabine	Cytarabine 1,500 mg/m ²	Cytarabine 1,000 mg/m ²
Mitoxantrone	Mitoxantrone 14 mg/m ²	NA

Low-Dose Arm

No dose reductions required.

APPENDIX C: EUROPEAN ORGANIZATION FOR RESEARCH AND TREATMENT OF CANCER QLQ-C30 QUESTIONNAIRE

EORTC QLQ-C30 (version 3)

We are interested in some things about you and your health. Please answer all of the questions yourself by circling the number that best applies to you. There are no "right" or "wrong" answers. The information that you provide will remain strictly confidential.

Please fill in your initials:

Your birthdate (Day, Month, Year):

31

Today's date (Day, Month, Year):

	Not at All	A Little	Quite a Bit	Very Much
1. Do you have any trouble doing strenuous activities, like carrying a heavy shopping bag or a suitcase?	1	2	3	4
2. Do you have any trouble taking a long walk?	1	2	3	4
3. Do you have any trouble taking a short walk outside of the house?	1	2	3	4
4. Do you need to stay in bed or a chair during the day?	1	2	3	4
5. Do you need help with eating, dressing, washing yourself or using the toilet?	1	2	3	4

During the past week:

	Not at All	A Little	Quite a Bit	Very Much
6. Were you limited in doing either your work or other daily activities?	1	2	3	4
7. Were you limited in pursuing your hobbies or other leisure time activities?	1	2	3	4
8. Were you short of breath?	1	2	3	4
9. Have you had pain?	1	2	3	4
10. Did you need to rest?	1	2	3	4
11. Have you had trouble sleeping?	1	2	3	4
12. Have you felt weak?	1	2	3	4
13. Have you lacked appetite?	1	2	3	4
14. Have you felt nauseated?	1	2	3	4
15. Have you vomited?	1	2	3	4
16. Have you been constipated?	1	2	3	4

Please go on to the next page

During the past week:	Not at All	A Little	Quite a Bit	Very Much
17. Have you had diarrhea?	1	2	3	4
18. Were you tired?	1	2	3	4
19. Did pain interfere with your daily activities?	1	2	3	4
20. Have you had difficulty in concentrating on things, like reading a newspaper or watching television?	1	2	3	4
21. Did you feel tense?	1	2	3	4
22. Did you worry?	1	2	3	4
23. Did you feel irritable?	1	2	3	4
24. Did you feel depressed?	1	2	3	4
25. Have you had difficulty remembering things?	1	2	3	4
26. Has your physical condition or medical treatment interfered with your family life?	1	2	3	4
27. Has your physical condition or medical treatment interfered with your social activities?	1	2	3	4
28. Has your physical condition or medical treatment caused you financial difficulties?	1	2	3	4

For the following questions please circle the number between 1 and 7 that best applies to you

29. How would you rate your overall health during the past week?

1 2 3 4 5 6 7

30. How would you rate your overall quality of life during the past week?

1 2 3 4 5 6 7

© 2001-2005 <http://www.maths.tcd.ie/~mkennedy/>

Aaronson, N.K., et al., *The European Organization for Research and Treatment of Cancer QLQ-C30: a quality-of-life instrument for use in international clinical trials in oncology*. J Natl Cancer Inst, 1993. **85**(5): p. 365-76.

APPENDIX D: PATIENT PREFERENCE FOR TREATMENT ASSIGNMENT SURVEY

We would like to understand whether patients and their doctors are comfortable letting a “coin flip” decide whether lower- or higher-intensity chemotherapy is used. We also want to understand how you made this decision, and why. Please answer the following questions:

1) Preference for treatment assignment

After thinking about this study and discussing it with your doctor(s), how do you prefer to be treated?

- I am willing to let a coin flip (i.e. computer program) decide whether I receive lower- or higher intensity chemotherapy
- I would like to make the decision whether I receive lower- or higher-intensity chemotherapy myself
 - My preference is to receive **lower**-intensity chemotherapy
 - My preference is to receive **higher**-intensity chemotherapy

2) How did you make this decision?

- I made the final decision about which treatment I would receive
- I made the final decision of my treatment after seriously considering my doctor's opinion
- My doctor and I decided together which treatment is best for me
- My doctor made the decision after seriously considering my opinion
- My doctor made the final decision about which treatment I would receive

3) Which factors were most important for you in making this decision?

Patient name/signature: _____

Date: _____

